The purpose of this study is to assess the effectiveness of ITU in the treatment of CPF by comparing pain, function, and change in plantar fascia thickness in subjects treated with ITU in addition to standard of care to subjects that are treated with standard of care alone. The primary outcome measure will be a computer adaptive questionnaire where pain, function and level of activity will be compared between the two groups. In addition, with the use of diagnostic ultrasound, plantar fascia thickness and presence or absence of hyper-echoic lesion will be compared between the two groups. Finally, the safety and tolerability of ITU will be monitored through the course of the study. It is hypothesized that patients receiving ITU in addition to standard of care will have a more rapid resolution of their pain, faster return to activities, and a greater decrease in plantar fascia thickening on ultrasound as compared to those only receiving standard of care.

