Assessment of Safety and Tolerability (Aim 3). Subject self-assessments of treatment tolerability will be conducted immediately after, two days after (phone survey) and two weeks after treatment using a 10-point visual analog scale (VAS, see Appendix 1-C). The subject will be asked to report their current level of pain and the maximum level of pain experienced over the last two days. The VAS is the standard for assessing pain for both clinical and research purposes. Recording of adverse events will take place at all visits (see adverse event reporting form Appendix 4 in the protocol). Adverse events and serious adverse events will be monitored throughout the study. A treatment will not be administered if there is residual pain/discomfort experienced by the subject from the previous treatment.

Statistical analysis. Data will be assessed for variance homogeneity and normality. FFI-P, PFCAT, and FAAM scores before and after intervention will be compared between the two groups using a paired t-test. Additionally, the mean thickness of the plantar fascia will be compared between the two groups before and after treatment and significance determined utilizing paired t tests. P<0.05 is considered to be statistically significant.

8) Risks to subjects

Exposure to ITU may produce short-term sensations which may cause discomfort and mild erythema for up to a few hours following the exposure. No detrimental side effects have been reported in previous clinical trials investigating similar devices in which ultrasound energy was applied to the neck and face. Additionally, the ITU in this investigation will utilize lower power parameters than those reported for these similar devices. We are seeking classification of the GEN II system (Guided

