## Statistical Approach

- Pain Reduction:

Pain level at the plantar fascia was self-reported by subjects at pre-treatment (used as baseline measurement) and again at each follow-up - 4, 8, 12, and 26 weeks - after initial treatment. The pain scale subjects used to identify their level of pain was a 10-point pain scale range, where 0 = no pain, 1 = slight pain through 10 which equates to the patient's worst imaginable pain. The goal for all subjects in the treatment group was to reduce pain by at least 25%. Pain scores reported at follow-up timepoints were compared to baseline score for each subject to determine if the goal was met by dividing the difference in the follow-up and baseline pain score by the baseline pain score. The percentage of subjects that met the pain reduction goal was calculated at each timepoint for both control/sham-treated and treatment groups by dividing the number of subjects that achieved the pain reduction goal at each timepoint by the total number of patients that gave a pain score for that time point.

- Plantar Fascia Hypoechoic Lesion Size:

A large proportion of patients suffering from chronic plantar fasciitis present with hypoechoic lesions in or around the proximal plantar fascia, as viewed by diagnostic ultrasound imaging[7].

Hypoechoic lesions were imaged and volumes were calculated at the baseline visit and each follow-up visit by measuring the inferior-to-superior and posterior-to-anterior radii in the long axis and the medial-to-lateral radius of the transverse axis and applying the following formula for the volume of an ellipse:

$$\text{Volume} = (4/3)\pi \cdot r_1 \cdot r_2 \cdot r_3$$

With  $r_1$ ,  $r_2$ , and  $r_3$  representing the three radii detailed above. Changes to lesion volumes were recorded at each follow-up timepoint and compared to baseline by dividing the volume of the lesion at that timepoint with the volume of the same lesion at pre-treatment baseline.

- Foot Function Index Score Reduction:

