In addition to the 11-point VAS pain scale, patients self-reported answers to questions from the Foot Function Index (FFI) pain subscale questionnaire, which has been standardized in a number of PF-focused publications [8-10]. Scores range from 0-90, with 0 indicating no pain and 90 indicating the worst pain imaginable in a variety of daily activities involving use of the plantar fascia. Self-reported scores were taken at baseline and each follow-up timepoint. The average score for each timepoint were calculated, and follow-up averages were compared to baseline to calculated the percentage reduction in score.

- Statistical Calculations

Student T-tests were utilized to determine statistically significant differences between baseline and subsequent follow-up measurements for self-reported and lesion size measurements. The level of significance ( $\alpha$ ) was set to 0.05.

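### The SAP tests three outcomes at four visits against baseline, each at 0.05, with no primary, adjusted or between-arm test, and leaves out the protocol's primary outcome

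*SAP*

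**What the plan says.** The SAP (Statistical Approach) describes three measured outcomes:

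- Pain on a 0-10 scale: "Pain level at the plantar fascia was self-reported by subjects at pre-treatment" and then at "4, 8, 12, and 26 weeks".
- Lesion volume, compared with baseline at each follow-up.
- The FFI pain subscale: "Self-reported scores were taken at baseline and each follow-up timepoint".

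Under Statistical Calculations it gives one rule for testing: "Student T-tests were utilized to determine statistically significant differences between baseline and subsequent follow-up measurements for self-reported and lesion size measurements". The significance level "was set to 0.05". The SAP names no primary outcome, primary visit, order of testing or multiplicity adjustment, and no test of one arm against the other. The percentage of subjects reaching the pain goal is reported for both arms, but no test of it is stated.

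The protocol (Section 3, Lay Summary) does name a primary measure: "The primary outcome measure will be a computer adaptive questionnaire where pain, function and level of activity will be compared between the two groups". Under Procedures, Patient Reported Outcome Measures, the computer-adaptive instrument described is the PROMIS PF CAT. The Statistical analysis paragraph lists FFI-P, PFCAT, FAAM and fascia thickness together, gives none of them priority or a visit, and ends: "P<0.05 is considered to be statistically significant". It intends a comparison of the two groups. The SAP contains neither that comparison nor the PF CAT.

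**The concern.** The protocol's primary objective is efficacy, so the reader will want to conclude that ITU does or does not add to standard care. Under this plan no single test answers that. Several outcomes at several visits each get their own 5% chance of a false positive, and a claim could rest on whichever is significant. In addition, the tests ask whether patients changed from baseline. In a sham-controlled trial where everyone gets active care, that is a different question from whether ITU works. A positive finding could therefore be chance, or the effect of standard care, and the stated 0.05 would protect against neither.

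**Working it through.** **Inputs.**
- Level per test: 0.05 (SAP, Statistical Calculations). Sidedness is not stated; two-sided is assumed. The documents give no familywise error rate to reproduce; one test has error 0.05 by definition.
- Outcomes 3, follow-up visits 4 (SAP). So 3 × 4 = 12 tests in one arm, and 24 if both arms are tested.
- Sample size 50, allocated 1:1 (protocol, Study Population; Randomization and Blinding), taken as 25 per arm.
- Correlations between outcomes and between visits: not given. Assumed 0.3-0.7 between outcomes and 0.5-0.8 between visits.

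**Step 1. No change from baseline, independent tests.** The chance of at least one significant result among m tests is 1 − 0.95^m.
- ITU arm, m = 12: 1 − 0.540 = 46%.
- Both arms, m = 24: 1 − 0.292 = 71%.

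These count significance in either direction. Counting only improvement, each two-sided test contributes 0.025, and 12 tests give 1 − 0.975^12 = 26%, against 2.5% for one test.

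**Step 2. No change from baseline, correlated tests.** Simulating the test statistics over the assumed correlations:
- 12 tests: about 24-38%.
- 24 tests: about 41-62%.

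Using paired t-tests with 25 per arm instead of normal statistics moves these ends by about one percentage point.

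**Step 3. No ITU effect, but both arms improve.** Both arms receive an NSAID, heel cups and physical therapy (protocol, Procedures), and the Background says initial conservative care works in 90% of patients in under 12 months. Improvement without any ITU effect is therefore expected. Its size is not given, so a common improvement of 0.2, 0.3 or 0.5 SD of the change score is assumed for all outcomes and visits, with correlations of 0.3 between outcomes and 0.5 between visits.

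| Assumed improvement | One test against baseline | At least one of 12, ITU arm | At least one of 24, both arms |
|---|---|---|---|
| 0.2 SD | 16% | 71% | 91% |
| 0.3 SD | 30% | 89% | 99% |
| 0.5 SD | 67% | over 99% | about 100% |

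The both-arms column follows from the ITU-arm column; at 0.2 SD, 1 − (1 − 0.71)² ≈ 0.91-0.92.

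**Step 4. Would adjusting alpha help?** Bonferroni at 0.05/12 = 0.0042 holds the error at or below 5% for the null of no change over time. It does not do so for the null of no ITU effect. The first column shows why: even a single pre-named baseline comparison, with no multiplicity at all, is significant in 16-67% of trials in which ITU does nothing. The contrast has to change, not only the cut-off.

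**Step 5. The protocol's own list.** Four outcomes at a single visit give 1 − 0.95^4 = 18.5% if independent, and about 13-17% with outcome correlations of 0.3-0.7. The protocol names no visit for these tests, so no larger count is used here.

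**The case against.** The protocol calls this a pilot study of 50, and strict familywise control is not always expected of a pilot. That carries some weight, but the primary objective is efficacy, the hypothesis is directional, and both documents set a significance threshold. If the study is exploratory, the documents should say so and drop significance claims.

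A reader might infer that every outcome, visit and arm is tested, so that a false claim for ITU has a chance of about 40-70%. The documents do not support that reading:
- The SAP sentence on t-tests does not mention arms. Testing within the sham arm is an inference, and a significant change there could not be offered as evidence for ITU. The relevant count is 12, not 24.
- The 40-70% range applies only if nobody in either arm changes over time, which the protocol's own account of standard care makes implausible.
- Multiplying the protocol's four outcomes by all its follow-up visits is likewise a reading. Its statistics paragraph speaks only of before and after, and Table 1 schedules no diagnostic ultrasound at 24 weeks.
- Nothing shows that a favourable result was in fact selected.

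Two further points stand. The choice of 12 weeks is a judgement, and a single 12-week contrast does not test the hypothesis of faster recovery. Naming a primary test after seeing data would not restore the 5% level.

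**Conclusion.** The concern holds in this form. The SAP's analysis has no test that carries a 5% error rate for the question the trial asks, and it omits the outcome the protocol calls primary. With no change from baseline, the ITU arm's 12 tests give at least one significant result with probability 46% if independent, and about 24-38% under the assumed correlations. If the sham arm is tested too, which the SAP does not state, the figures are 71% and about 41-62%. With no ITU effect but an assumed shared improvement of 0.2-0.5 SD, they are about 71-99% in the ITU arm and 91-100% across both. All figures other than the independence values depend on assumed correlations, the last set also on an assumed improvement and 25 per arm. The conclusion does not depend on their exact values: the missing between-arm test is the main defect, and multiplicity adds to it.

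**What to change.** - Let one test carry the 0.05: the between-arm difference in PROMIS PF CAT, adjusted for baseline, at one named visit. Twelve weeks is a reasonable choice because it is the latest visit common to both schedules and matches the 3-month commitment in the recruitment text. What matters is that one visit is fixed.
- Restore PF CAT to the SAP, and state in the protocol that it is the computer-adaptive primary measure.
- Report all other outcomes, visits and within-arm changes as estimates with 95% confidence intervals and no significance claim. Alternatively, apply Holm across one between-arm comparison per secondary outcome.
- Reconcile the follow-up schedules: 2, 4, 6, 12 and 24 weeks in the protocol, against 4, 8, 12 and 26 in the SAP.

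The cost is that fewer results can be called significant. The protocol already schedules the questionnaire, so no new data collection is planned by this change, but the sponsor must confirm that PF CAT was collected at the chosen visit. The SAP is written in the past tense. If outcome data had been seen when the primary test is chosen, that test must be labelled post hoc.
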